The scientific rationale for secondary endpoints is as follows:

- EBA as assessed by alternative methods [TTP in MGIT culture and LAM assay]. MGIT culture and LAM assay are easier to conduct compared to solid media culture. Hence, insight into the suitability of such methods to replace solid media culture will be useful for this and other TB drug development programs.
- Full AE assessment. All AE will be assessed by seriousness, intensity (severity), relationship to study drug and expectedness based on the information provided in the

Investigator Brochure and summarized by body system and preferred medical term. This will allow the full safety and tolerability profiling of TBA-7371.

- Assessment of heart rate and blood pressure via vital signs and ECG, eye symptoms, visual acuity and color vision. These measurements were selected based on the safety profile that emerged from animal studies and from phase 1 study TBA7371-001 (see above). Multiple assessment methods will be carried out for cardiovascular variables to maximize the sensitivity of the study. Eye symptoms will be assessed by non-leading questions delivered by trained staff based on a standardized script. Visual acuity and color vision will be assessed through standardized procedures. The possibility of decrease (tachyphylaxis) or increase over time of these unwanted effects, as well as their persistence or recurrence in the month following discontinuation of study drug, will also be assessed: results of study TBA7371-001 suggest changes over time during treatment with TBA-7371 of cardiovascular (decrease) and eye (increase) adverse events. It should be noted that all eye symptoms reported study TBA7371-001 were transient.

PK profile and relationship between exposure and magnitude of EBA. So far, the PK profile of TBA-7371 has been only studied in animals and in healthy volunteers. This study allows the confirmation of the PK profile in TB patients. The relationship between exposure and bactericidal response will guide the selection of the dose regimen(s) for further development of TBA-7371. No active metabolite of TBA-7371 has been identified so far, and no major metabolite seen in humans has been detected at more than 10% of parent TBA-7371. Therefore, TBA-7371 metabolism will not be examined further in this study.

Additional measurements may be added as exploratory endpoints. Exploratory endpoints will be the object of separate documents.

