Table 2. Secondary Objectives and Endpoint

	
 Manual HR, SBP and DBP from vital signs, after 2 (± 0.5) minutes in standing position (“manual, 2-minute standing”); HR from ECG, supine position (“ECG, supine”) Change in frequency of participants with eye symptoms (all, severe, serious) and change in mean visual acuity score and frequency of color vision abnormalities (tritan, protan, deutan) in one or both eyes and degree of severity (mild, moderate, and severe) from Screening to Days 28 and 42 and from Days 1-15 (combined) to Days 28-42 (combined).
Assess whether there are meaningful changes in safety laboratory measurement	
For each blood/serum and urine parameter:
 
 Mean, median, highest and lowest value. Shift tables from Screening to Day 3, Day 7, Day 14, and Day 42.
Secondary, PK and PK/PD	
Evaluate the pharmacokinetics of TBA-7371 monotherapy over the 14-day treatment period.	TBA-7371 concentration profiles and PK parameters over the 14-day treatment interval: C_{max} , T_{max} , C_{last} , T_{last} , AUC_{inf} , $AUC_{1\text{ st}}$, AUC_{tau} , C_{min} , half-life, accumulation ratios.
Identify the lowest exposure to of TBA-7371 associated with maximal EBA effect.	Expected concentration associated with 90% of the maximal TBA-7371 EBA effect (EC_{90}).

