13.1 TBA-7371 Pharmacokinetics

Timing of TBA-7371 sampling for participants randomized to TBA-7371 will be as follows:

	QD Dosing	BID Dosing	TID Dosing
Screening Phase	Predose	Predose	Predose
Study Treatment Phase	
 Predose on Days 1, 2, 4, 7, and 14. 30 min, 1h, 2.5h, 3h, 4h, 6h, 7h, 10.5h, 12h, and 16.5h on days 1, 7, and 14. 	
 Predose on Days 1, 2, 4, 7, and 14. 30 min, 1h, 2.5h, 3h, 4h, 6h, 7h, 10.5h, and 12h on days 1, 7, and 14. 	
 Predose on Days 1, 2, 4, 7, and 14. 30 min, 1h, 2.5h, 3h, 4h, 6h, and 7h on days 1, 7, and 14.

TBA-7371 concentrations below the limit of quantitation will be set to 0. TBA-7371 concentrations will be summarized by treatment group using nominal time points for all participants in the PK population. The following descriptive statistics will be provided: N, arithmetic mean, standard deviation, arithmetic percent coefficient of variation (CV), median, minimum, maximum, geometric mean, and geometric percent CV. Linear and semi-log plots of individual and mean concentrations versus nominal time will be presented by treatment group. Plasma concentration of TBA-7371 having value 0 will be excluded from semi-log plots.

The following PK parameters of Days 1, 7, and 14 will be derived using non-compartmental model.

Day 1	Day 7	Day 14
C _{max} , T _{max} , C _{last} , T _{last} , AUC _{inf} , AUC _{last} , AUC _{tau} , C _{min} , half-life,	C _{max} , T _{max} , C _{last} , T _{last} , AUC _{inf} , AUC _{last} , AUC _{tau} , C _{min} , half-life, accumulation ratio (C _{max} of day 1/C _{max} of day 7)	C _{max} , T _{max} , C _{last} , T _{last} , AUC _{inf} , AUC _{last} , AUC _{tau} , C _{min} , half-life, accumulation ratio (C _{max} of day 1/C _{max} of day 14)

- C_{max} – maximum plasma concentration
- C_{min} – minimum plasma concentration
- T_{max} – time to maximum plasma concentration

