13.3 Exposure-Response Analysis

The exposure-response E_{max} model will be used to estimate EC_{90} as follows:

$$BA_{CFU}(0-14) = \frac{E_{max} \cdot C_{max(ss)}}{EC_{50} + C_{max(ss)}} + \varepsilon$$

where:

- $BA_{CFU}(0-14)$ is the average change in log(CFU) counts over each day from screening to day 14.
- E_{max} is the maximal TBA-7371 EBA effect.
- EC_{50} is the expected concentration of TBA-7371 associated with 50% of E_{max} .
- $C_{max(ss)}$ is the steady state C_{max} of TBA-7371 measured at day 14.
- ε is a random error assumed to be normally distributed with mean zero and constant variance σ^2 .

Exposure-response analysis will be performed in the PK population with participants having PK data measured on day 14. The SAS PROC NLMIXED procedure will be used to fit an E_{max} model. Maximum likelihood estimates and corresponding 95% CIs for E_{max} and EC_{50} will be provided. The prediction of EC_{90} to reach 90% of E_{max} is computed as

$$EC_{90} = 9 \cdot EC_{50}$$

95% CI for the estimate of EC90 will be provided. An exposure-response curve of E_{max} model will be produced and vertical reference lines for EC₅₀ and EC₉₀ will be provided for each treatment group as well as overall.

Alternative sigmoid exposure-response model may be explored if deemed appropriate.

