12. **Overnight sputum collection for EBA assessment and exploratory measurements.** Overnight[†] sputum will be collected from 3 PM to 7 AM of the following Day (16 hours) on Days -2 and -1 during Screening Phase and on 14 consecutive Days during the Study Treatment Phase (Days 1 to 14) for EBA assessment. The last collection will finish at 7 AM of Day 15. [†]Ability to sting for isoniazid and rifampicin, and minimum inhibitory concentrations (MIC) of TBA-7371 will be performed on either of Day -2 or Day -1 and again on Day 14.

13

14. Recording of AE, SAE (including serious ADR) and AESI; recording of concomitant treatments. Adverse events (AE), serious adverse events (SAE), including serious adverse drug reactions (ADR), adverse events of special interest (AESI) and concomitant treatments will be recorded from the time each participant has signed the informed consent form (ICF) until he/she has completed the last follow-up visit (Day 42) or the Early Withdrawal Visit (EWV).

15. **Blood/serum sample collection for PK measurements.** WILL BE CONDUCTED ONLY IN PARTICIPANTS RANDOMIZED TO TBA-7371. Timing of sampling will be as follows:

- Study Treatment Phase: Days 1, 2, 4, 7 and 14 before administration of the 1st daily dose of study drug; in addition, on Days 1, 7 and 14 samples will also collected 30 min (+/- 5 min) and at 1h, 2.5h, 3h, 4h, 6h, 7h, 10.5h, 12h, 16.5h (+/- 15 min) after 1st daily dose of study drug. (see Table 4 of the protocol). Patients assigned to BID dosing will not have collections at 16.5h, and the 12h sample will be taken prior to the second daily dose. Patients assigned to TID dosing will not have collections at 10.5h, 12h and 16.5h, and the 7h sample will be taken prior to the second daily dose.

When timing coincides, samples must always be taken after recording of ECG and vital signs.

16

Coronavirus Disease (COVID-19) / Severe Acute Respiratory Syndrome Coronavirus 2 (SARS-CoV-2 Testing). COVID-19 testing will be conducted via PCR using a test product authorized by SAHPRA at an accredited public or private sector laboratory. A specimen will be collected during the screening period between Day-7 to Day -3, and a negative result must be confirmed prior to randomization. For safety monitoring purposes, testing will also be performed at Day 7 (± 2 Days), on Day 14 OR Day 15 before discharge, and/or at any other time that infection is suspected.

Approved

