Appendix 4 SAS Code

SAS code for computing 95% confidence interval for single proportion based on the mid-P method:

```
proc freq data=<dataset> order=freq;
  tables category / binomial (CL=MIDP) alpha=0.05;
  weight Count;
run;
```

SAS code for response-exposure E_{max} model:

```
ods output fitstatistics=<Data with aic>;
ods output parameterestimates=<Data with slope estimates>;
proc nlmixed data=<dataset>;
  by <treatment group>;
  parms Emax=<numeric>
    EC50=<numeric>
    s2=<numeric>;
  mu=(Emax*Cmax) / (EC50+Cmax);
  model <Avg. Slope(0-14)> ~ normal(mu,s2);
run;
```

SAS code for bilinear regression model with κ as one of the parameters:

```
ods output fitstatistics=<Data with aic>;
ods output parameterestimates=<Data with slope estimates>;
ods output additionalestimates=<Data with BA(0-14) estimate>;
run;
proc nlmixed data=<dataset>;
  by <subject ID>;
  parms alpha=4 to 8 by 0.5    betal=-0.3 to 0.3 by 0.05
beta2=-0.3 to 0.3 by 0.05    kappa=2 to 10 by 1    s2=0.05 to 0.3
by 0.05 / best=1;
  bounds alpha >0,    1 < kappa < 14,    s2>0; * Add constraints to
parameters to improve convergence;
  if day <= kappa then mu = alpha + betal*day;
  else if day > kappa then mu = alpha + betal*kappa +
beta2*(day-kappa);
  model logCFU ~ normal(mu,s2);
  estimate 'BACfu(0-14)' (kappa*betal + (t_last-
kappa)*beta2)/t_last; *Estimate BA(0-14);
run;
```

SAS code for bilinear regression model with kappa fixed at 2:

```
ods output fitstatistics=<Data with aic>;
ods output parameterestimates=<Data with slope estimates>;
proc nlmixed data=<dataset>;
  by <subject ID>;
  parms alpha=4 to 8 by 0.5    beta1=-0.3 to 0.3 by 0.05
beta2=-0.3 to 0.3 by 0.05 s2=0.05 to 0.3 by 0.05 / best=1;
  bounds alpha >0,    s2>0; * Add constraints to parameters to
improve convergence;
  if day <= 2 then mu = alpha + beta1*day;
  else if day > 2 then mu = alpha + beta1*2 + beta2*(day-2);
  model logCFU ~ normal(mu,s2);
run;
```

SAS code for simple regression model:

```
ods output fitstatistics=<Data with aic>;
ods output parameterestimates=<Data with slope estimates>;
proc nlmixed data=<dataset>;
  by <subject ID>;
  parms alpha=4 to 8 by 0.5    beta1=-0.3 to 0.3 by 0.05    s2=0.05
to 0.3 by 0.05 / best=1;
  mu = alpha + beta1*day;
  model logCFU ~ normal(mu,s2);
run;
```

SAS code for ANCOVA (lsmeans statement used to estimate 90% CIs, lsmestimate statements used for one-sided 5% p-values, trt = treatment group with HRZE as reference):

```
proc mixed data=<dataset>;

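### SAP 13.1 inverts the accumulation ratio, and SAP 13.3 does not say whether the pooled or the by-regimen Emax fit supplies the EC90 endpoint, while its only code fits one regimen at a time

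*SAP*

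**What the plan says.** **Accumulation ratio.** Accumulation ratios are among the PK parameters listed as a secondary endpoint (Protocol Table 6, SAP Table 2). The protocol gives no formula. The parameter table in SAP 13.1 does: after "half-life, accumulation ratio" it prints, in parentheses, Cmax of Day 1 divided by Cmax of Day 7, and in the next column Cmax of Day 1 divided by Cmax of Day 14.

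**EC90.** The PK/PD objective is "Identify the lowest exposure to of TBA-7371 associated with maximal EBA effect", and its endpoint is "Expected concentration associated with 90% of the maximal TBA-7371 EBA effect". SAP 13.3 estimates it from an Emax model of BA_CFU(0-14) on Day 14 Cmax, with EC90 = 9 × EC50 and 95% CIs. On who is analysed it says "Exposure-response analysis will be performed in the PK population with participants having PK data measured on day 14". The curve with its EC50 and EC90 lines "will be provided for each treatment group as well as overall". Neither SAP 13.3 nor Protocol Table 9 says which of these fits is the endpoint estimate. SAP Appendix 4 holds one block of Emax code. It contains the line "by <treatment group>", and EC50 has no lower bound, although the bilinear code in the same appendix does bound its parameters.

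**PK population.** Protocol Table 8 asks for at least one dose and one measurable sample. SAP Table 6 asks for at least one dose and a measurable pre-dose and post-dose pair. SAP section 8 says that the planned analyses have not changed.

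**The concern.** An accumulation ratio is ordinarily read as later over first, with values above 1 meaning that drug builds up. The SAP formula gives the reciprocal, so a table filled in as specified would show accumulation as a number below 1.

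The EC90 endpoint answers one question about TBA-7371, and the design supplies a four-fold range of single-dose sizes (100 to 400 mg) with which to answer it. A fit within one regimen sees only the spread of Cmax between people on the same dose. If by-regimen and overall EC90s are all produced and none is designated in advance, the report may carry up to six values with no pre-specified choice among them, five of them close to uninformative. Protocol 4.2 says that the relationship between exposure and bactericidal response "will guide the selection of the dose regimen(s) for further development of TBA-7371", so the choice has a use beyond description.

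**Working it through.** **1. Accumulation ratio.** Let R = Cmax(Day 7) / Cmax(Day 1). SAP 13.1 computes 1/R. For R = 1.5 it gives 1/1.5 = 0.67; for R = 2 it gives 0.50. The Day 14 column behaves the same way.

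**2. Figures in the plan.** The documents give no precision figure for EC90. Two figures that feed the check do reproduce:
- Slope SD 0.1, n = 15, one-sided alpha 5% (SAP 6.2). One-sample noncentral t power is 79.4% for a reduction of 0.067 and 89.7% for 0.079, against the stated 80% and 90%.
- Setting C/(EC50 + C) = 0.9 gives C = 9 × EC50, as in SAP 13.3. The relative error of EC90 is therefore that of EC50.

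**3. Inputs.** From the documents: 15 participants in each of 5 regimens (75 pooled); SD 0.1, with 0.05 as the lower end of the cited range 0.05–0.08. Assumed, because the documents give no Cmax, exposure CV or Emax for TBA-7371: Emax 0.112 (the largest reference reduction in Protocol 9.2; SAP 6.2 prints 0.122 for the same arm), lognormal exposure with CV 40%, single-dose Cmax of 1, 1, 2, 1, 4 for 100 QD, 100 BID, 200 QD, 100 TID, 400 QD in units of the 100 mg QD value, and a true EC90 of 2.7 or 9 units (EC50 0.3 or 1).

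**4. Why one regimen is not enough.** The model has no baseline term. To locate EC50, the data must therefore tell the curve from a flat line (EC50 towards 0) and from a straight line through the origin (EC50 towards infinity).
- CV 40% gives a log-scale SD of √ln(1 + 0.4²) = 0.385. The 10th to 90th percentile of Cmax at 100 mg is exp(±1.28 × 0.385) = 0.61 to 1.64.
- With EC50 = 1, the effect at those points is 0.112 × 0.61/1.61 = 0.042 and 0.112 × 1.64/2.64 = 0.070. The whole contrast is about 0.027, roughly a quarter of one SD of 0.1, in 15 people.
- Pooled, exposure reaches 4 × 1.64 = 6.56, where the effect is 0.112 × 6.56/7.56 = 0.097. The contrast is about 0.055, in 75 people.

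**5. Simulation.** 1,500 trials per scenario, least squares with EC50 profiled from 0.001 to 1,000. Ranges cover both EC90 values and an effect driven by either Cmax or daily AUC, with each fit using the driving metric.

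| Result | SD | By regimen | Pooled |
|---|---|---|---|
| EC90 within two-fold, Emax 0.112, CV 40% | 0.1 | 8–12% | 29–44% |
| | 0.05 | 17–23% | 56–75% |
| EC90 within two-fold, Emax 0.112–0.15, CV 20–60% | 0.1 | 4–21% | 27–60% |
| | 0.05 | 8–40% | 50–89% |
| 95% profile CI finite at both ends, same wider set | 0.1 | 0–1% | 2–57% |
| | 0.05 | 0–13% | 22–99% |

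At SD 0.1, EC50 ran to an edge of the search grid in 38–81% of by-regimen fits across the wider set.

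A separate Fisher-information calculation (Emax 0.15, CV 30–50%, EC50 0.5–2 units) gave a relative standard error of EC90 of 287–866% by regimen against 88–112% pooled at SD 0.1, and 143–435% against 43–56% at SD 0.05.

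**The case against.** **The pooled fit is already planned.** A reader might infer from Appendix 4 that the plan has no pooled EC90. The documents do not support that. SAP 13.3 describes one model in the PK population with Day 14 data and asks for overall output, Protocol 9.5 combines the groups for its graphical exploration of PK against CFU, and the appendix code is a template with placeholders. What stands is narrower: the pooled fit has no code and is not named as the endpoint analysis. The absence of a separate EC90 line in the code matters little, since its limits are nine times those of EC50.

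**The sizes are assumed, and pooling is no cure.** Both are true. One of the two EC90 values (9) lies outside the tested exposure range of 1–4, and the pooled interval is often open at SD 0.1. The by-regimen fit was nevertheless much worse in every scenario run.

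**The inverted ratio can be recovered.** The formula is printed, and Cmax is summarised by day, so a careful reader could turn the ratio over. It is still wrong as specified.

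**Is Cmax the wrong metric?** For TID dosing, "the 7h sample will be taken prior to the second daily dose", so Day 14 Cmax reflects the first daily dose. A reader might infer that the Emax model should use daily AUC. The documents do not settle this. The endpoint is worded as a concentration, SAP 13.2 already correlates AUCinf and T>MIC with CFU overall, and any bias depends on a half-life and an exposure driver that the documents do not give.

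**Does the SAP PK population lose particular participants?** That might be inferred by reading the pair as same-day, with post-dose samples only on Days 1, 7 and 14. SAP Table 6 does not say same-day, Protocol Table 4 has an early-withdrawal PK sample, Protocol 8.7 lists one on Day 15, and no quantification limit is given. SAP Appendix 5 records the change as a clarification. Only the mismatch in wording, and the silence of section 8, stands.

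**Conclusion.** The accumulation ratio in SAP 13.1 is wrong as written. It is the reciprocal of the quantity it names, so 1.5-fold accumulation is reported as 0.67. This needs no assumption.

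The EC90 analysis is under-specified. SAP 13.3 plans by-regimen and overall output without designating either as the endpoint, and the only code produces the by-regimen fits, whose EC90 is practically non-identifiable. Under the assumed values, the chance of an EC90 within two-fold of the truth is about 10% by regimen against 30–45% pooled at SD 0.1, and about 20% against 55–75% at SD 0.05. The direction held throughout; the percentages rest on an Emax, an exposure CV and dose proportionality that are not in the documents. Even the pooled EC90 stays imprecise at the design SD of 0.1.

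EC90 is a secondary endpoint with no success rule, and Protocol 4.2 ties regimen selection to the exposure-response relationship without naming EC90. These points should be corrected, but they do not touch the primary analysis. The PK population mismatch is a minor matter of wording.

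**What to change.** 1. In SAP 13.1, define the accumulation ratio as Day 7 (or Day 14) Cmax divided by Day 1 Cmax.
2. In SAP 13.3, name the pooled fit over all TBA-7371 participants with Day 14 PK data as the EC90 analysis. In Appendix 4, supply its code without the BY statement and with EC50 bounded above 0. Drop the by-regimen EC90s or label them descriptive.
3. Reconcile the PK population in SAP Table 6 with Protocol Table 8, or declare the change in SAP section 8.

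The cost is a few lines of SAP text and code; no new samples or data are needed. The pooled EC90 should be reported with its interval and with the plain statement that it may be wide.

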14 PHYSICAL EXAMINATION

Clinically significant physical examination findings will be provided in a listing.

15 CONCOMITANT MEDICATIONS

All concomitant medications will be coded using the World Health Organization Drug Dictionary, March 1, 2018 version or later. The Anatomical Therapeutic Chemical (ATC) Level 3 and preferred name will be used to list and summarize the data.

The frequency and percentage of participants taking concomitant medication will be summarized by drug class (ATC Level 3) and medication preferred term and by treatment group. Multiple concomitant medications usage by a participant in the same ATC category will be counted only once.

All concomitant medications will be provided in a listing.

17 APPENDICES

Appendix 1 Schedule of Activities

Assessments A ± 15-minute time window is allowed for all measurements	Screening Day ^a			Study Treatment Day												Follow-up Day ^b			EWV ^c		
	-7 to -3	-2	-1	1	2	3	4	5	6	7	8	9	10	11	12	13	14	15	28	42	
Written informed consent ¹	X																				
Hospital admission or discharge ²	X																		X		
Demography and medical and treatment history	X																				
Physical examination ³	X										X								X	X	X
Chest x-rays ⁴	X																				
Blood/serum sample collection for HIV test and CD4 count	X																				
Serum sample collection for pregnancy status assessment	X																	X	X	X	
Blood/serum sample collection for clin. safety lab assessment ⁵	X						X				X							X	X	X	
Urine sample collection for clinical safety lab assessment	X					X					X							X	X	X	
Urine sample collection for isoniazid and drug screening ⁶	X																				
Overnight sputum collection for eligibility asses. (volume, acid-fast bacilli Mtb pos. and rifampicin sensitivity) ⁷	X																				
Vital signs and body weight recording ⁸	X				X	X	X	X	X	X	X	X	X	X	X	X	X	X	X	X	X
ECG recording ⁹	X				X		X		X		X		X		X		X	X	X	X	X
Eye assessment (visual acuity, color vision, symptoms) ¹⁰	X			X		X		X		X		X		X		X	X	X	X	X	X

Assessments A ± 15-minute time window is allowed for all measurements	Screening Day ^a			Study Treatment Day												Follow-up Day ^b			EWV ^c		
	-7 to -3	-2	-1	1	2	3	4	5	6	7	8	9	10	11	12	13	14	15	28	42	
Study drug (IMP) administration ¹¹				X	X	X	X	X	X	X	X	X	X	X	X	X	X				
Overnight sputum collection for EBA & exploratory measures. ¹²		X	X	X	X	X	X	X	X	X	X	X	X	X	X	X	X				
Spot sputum collection for exploratory measurements ¹³			X	X	X	X	X	X	X	X	X	X	X	X	X	X	X				
Recording of AE, SAE (incl. serious ADR) and AESI ¹⁴	X	X	X	X	X	X	X	X	X	X	X	X	X	X	X	X	X	X	X	X	X
Recording of concomitant treatments ¹⁴	X			X	X	X	X	X	X	X	X	X	X	X	X	X	X	X	X	X	X
Blood/serum sample collection for PK measurements ¹⁵				X	X	X		X		X							X				
COVID-19/SARS-CoV-2 Testing ¹⁷		X								X								X			

a. **Screening (Days -7 to -1).** Screening procedures will be conducted during the up to 7-Day screening period. Screening assessments can be done at any time during this period, except for the written informed consent, which must be given before any screening is started, the overnight sputum collection for eligibility assessment, which must be completed on or before Day -3, and the overnight sputum collection for EBA, which must be done consecutively on Day -2 and Day -1. Subjects may be hospitalized for the entire screening period at the investigator's discretion, but must be hospitalized starting on Day -3.

b. **Follow-up (Days 15 to 42).** Allowed window for Day 28 and Day 42 visits: +/- 3 Days.

c. **Early Withdrawal Visit (EWV) or Unscheduled Visit.** Participants who withdraw before Day 14 will be asked to complete the EWV assessments within 2 Days of withdrawal. Participants who complete the Study Treatment Phase, but do not return for the Day 28 visit will be asked to return for the Day 42 visit. If access to sites is limited due to the local status of COVID-19 pandemic, the Day 28 and Day 42 visits could potentially be conducted by telephone. Procedures and assessments conducted during an unscheduled visit will be at the discretion of the investigator in consultation with the medical monitor.

1. **Written informed consent** will be given before any screening procedure is started.

2. **Hospital admission and discharge.** Study participants will be hospitalized by Day -3 of the Screening Phase and will remain in hospital until the Day after the last dose of study drug is dispensed (Day 15). Discharge from hospital will occur on Day 15 after all procedures planned for that Day are completed. Upon discharge, participants will be referred to the national TB treatment program for standard of care (SoC) treatment.
3. **Physical examination (PE).** Full PE will be conducted during the Screening Phase; focused PE (guided by medical history) will be conducted on Days 7, 15, 28, 42. Focused PE will be conducted at EWV if the participant discontinues between Day 1 and Day 14. Focused PE may be conducted during an unscheduled visit at the discretion of the investigator.
4. **Chest X-rays.** Good quality Posterior-Anterior chest X-rays will be accepted if conducted within 1 week prior to Day -7. If not available, chest X-rays will be conducted during the Screening Phase.
5. **Blood/serum sample collection for clinical safety laboratory assessment.** The Day 3 and 7 sampling will occur before the 1st dose of study drug.
6. **Urine sample collection drug screening:** cannabinoids, cocaine, amphetamines, opiates, methamphetamines.
7. **Overnight sputum collection for eligibility assessment.** Sputum assessment, including volume, will be performed by a Sponsor-approved central laboratory (see laboratory study instruction document). The 1st of the 3 overnight sputum collections (Day -7 to Day -3) conducted during the Screening Period will be used to assess eligibility as follows: sputum volume (must be at least 10 mL), acid-fast bacilli detection, *Mycobacterium tuberculosis* (Mtb) positivity and rifampicin sensitivity via the GeneXpert[®] diagnostic system (Cepheid). In case inclusion criteria cannot be met from the 1st overnight sputum collection, one or more of the above procedures can be conducted on a 2nd overnight sputum collected during the Day -7 to -3 screening period if the patient is domiciled at the site for both.
8. **Vital sign and body weight recording.** The following 5 vital signs will be recorded: axillary body temperature (BT), respiratory rate (RR), heart rate (HR), systolic blood pressure, (SBP), diastolic blood pressure (DBP). Body weight (BW) will also be recorded with vital signs. Vital signs and body weight will be recorded as follows:
 - Screening Phase: vital signs and BW once in the morning at approximately the same time the 1st daily dose study drug will be administered. SBP, DBP and HR can be repeated twice if exclusion criteria are met.
 - Study Treatment Phase: vital signs and BW once every morning (Days 1 to 14) before administration of the 1st daily dose of study drug; in addition, on Days 1, 4, 7, 10 and 14 vital signs will also be collected 2.5h, 10.5h and 16.5h after the time of 1st daily dose of study drug (see Table 4 of the protocol).
 - Follow-up Phase: vital signs and BW on Day 15 in the morning before 1st daily dose of SoC medication; on Days 28 and 42 during the visit.
 - EWV: vital signs and BW if the participant withdraws from the study between Day 1 and 14.At each time point BT, RR and BW will be measured once, whereas HR, SBP and DBP will be measured twice as follows: after 10 min supine ("manual, supine") and after 2 (± 0.5) min standing ("manual, 2-min standing"). When ECG, vital signs and/or blood/serum samples are to be obtained at the same time point, the following order must be followed: ECG, vital signs, blood/serum sample, within 5 min of each other.
9. **ECG recording.** 12-lead ECG will be recorded once at each time point after at least 10 minutes of supine rest as follows:
 - Screening Phase: once in the morning at approximately the same time the 1st daily dose study drug will be administered.
 - Study Treatment Phase: on Days 1, 4, 7, 10 and 14 before administration of the 1st daily dose of study drug and 2.5h, 10.5h and 16.5h thereafter (see Table 4 of the protocol).
 - Follow-up Phase: on Day 15 in the morning before 1st daily dose of standard of care medication; on Days 28 and 42 during the visit.

TBA-7371

Statistical Analysis Plan: Gates MRI-TBD03-201

Bill & Melinda Gates Medical Research Institute

04-October-2022

- EWV: if the participant withdraws from the study between Day 1 and 14.

10. Eye assessment. A trained staff member will assess: i) eye symptoms using a standardized script (Section 10.5, Appendix 5 of the protocol), ii) visual acuity by means of the Rosenbaum Pocket Eye Screener, iii) color vision by means of the Waggoner Computerized Color Vision Test and as follows:

- Screening Phase: once in the AM.
- Study Treatment Phase: Days 1, 4, 7, 10, and 14, 2.5h after 1st daily dose of study drug (see Table 4 of the protocol).
- Follow-up Phase: Days 15, 28 and 42 during the visit.
- EWV: if the participant withdraws from the study between Days 1 and 14.

11. Study drug (IMP) administration. Study drug (TBA-7371 or HRZE) will be administered from Day 1 to Day 14 based on the randomization list by an authorized and trained site staff member. The 1st dose of study drug will be administered at the same time each Day for the individual participant. Subsequent doses will be administered as follows (see Table 4 of the protocol):

- Twice daily (BID) schedules: 12h after 1st dose
- Three times (TID) daily schedule: 7h and 14h after 1st dose

Fasting must occur at least 2 hours before dosing and at least 1 hour after dosing. Study drug administration will be followed by 200 mL water.

12. **Overnight sputum collection for EBA assessment and exploratory measurements.** Overnight[†] sputum will be collected from 3 PM to 7 AM of the following Day (16 hours) on Days -2 and -1 during Screening Phase and on 14 consecutive Days during the Study Treatment Phase (Days 1 to 14) for EBA assessment. The last collection will finish at 7 AM of Day 15. [†]Ability to sting for isoniazid and rifampicin, and minimum inhibitory concentrations (MIC) of TBA-7371 will be performed on either of Day -2 or Day -1 and again on Day 14.

13

14. Recording of AE, SAE (including serious ADR) and AESI; recording of concomitant treatments. Adverse events (AE), serious adverse events (SAE), including serious adverse drug reactions (ADR), adverse events of special interest (AESI) and concomitant treatments will be recorded from the time each participant has signed the informed consent form (ICF) until he/she has completed the last follow-up visit (Day 42) or the Early Withdrawal Visit (EWV).

15. **Blood/serum sample collection for PK measurements.** WILL BE CONDUCTED ONLY IN PARTICIPANTS RANDOMIZED TO TBA-7371. Timing of sampling will be as follows:

- Study Treatment Phase: Days 1, 2, 4, 7 and 14 before administration of the 1st daily dose of study drug; in addition, on Days 1, 7 and 14 samples will also collected 30 min (+/- 5 min) and at 1h, 2.5h, 3h, 4h, 6h, 7h, 10.5h, 12h, 16.5h (+/- 15 min) after 1st daily dose of study drug. (see Table 4 of the protocol). Patients assigned to BID dosing will not have collections at 16.5h, and the 12h sample will be taken prior to the second daily dose. Patients assigned to TID dosing will not have collections at 10.5h, 12h and 16.5h, and the 7h sample will be taken prior to the second daily dose.

When timing coincides, samples must always be taken after recording of ECG and vital signs.

16

Coronavirus Disease (COVID-19) / Severe Acute Respiratory Syndrome Coronavirus 2 (SARS-CoV-2 Testing). COVID-19 testing will be conducted via PCR using a test product authorized by SAHPRA at an accredited public or private sector laboratory. A specimen will be collected during the screening period between Day-7 to Day -3, and a negative result must be confirmed prior to randomization. For safety monitoring purposes, testing will also be performed at Day 7 (± 2 Days), on Day 14 OR Day 15 before discharge, and/or at any other time that infection is suspected.

Approved

